### 2.2 Statistical Methods

Descriptive analysis will be performed to summarize baseline, clinical and safety event data. Depending on the type of data (e.g., continuous or categorical), statistical methods described in the following sections will be used.

#### 2.2.1 Descriptive Statistics for Continuous Variables

For continuous variables such as age, results will be summarized with the numbers of observations, means, standard deviations, and, if specified in the table mockups, with quartiles, minimums, and maximums.

#### 2.2.2 Descriptive Statistics for Categorical Variables

For categorical variables such as sex, NYHA, results will be summarized with subject counts and percentages/rates, and where specified in the table mockups, with exact 95% Clopper-Pearson confidence intervals. For binary variables such as adverse events, results will be summarized with patient counts, and percentages.

## Statistical Analysis Plan

### 2.3 Endpoint Analysis

#### 2.3.1 Primary Endpoint(s)

The primary endpoint is (the number of) successful implantation of the MitraClip NT device resulting in a decrease in the MR severity grade as assessed from the discharge echocardiogram (10-day echocardiogram will be used if discharge is unavailable or uninterpretable). Subjects who die or undergo mitral valve surgery before discharge will be considered a failure for the procedure. The primary analysis population is the ATP.

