2.2.4 Summary of Previous Clinical Studies

This section summarizes results of relevant studies of the MitraClip NT System Clinical Program. Please refer to the Investigator Brochure for a summary of the clinical investigations sponsored by Abbott and all published data on the MitraClip therapy in addition to the relevant previous clinical experience with medical devices that have similar characteristics, and the history of adverse device effects.

Rationale for the MitraClip NT System Russian Trial is subsequently presented in the context of this scientific body of evidence.

EVEREST I Design and Results

The EVEREST I Feasibility trial was the first prospective, multi-center, non-randomized trial to evaluate the preliminary safety and effectiveness of the percutaneous **MitraClip** System in patients with moderate-to-severe (3+) or severe (4+) MR in surgical candidates. After undergoing the **MitraClip** procedure, patients were followed at discharge, 30 days, 6, 12, 18 and 24 months and every year thereafter through 5 years. An independent Echocardiography Core Laboratory (ECL) assessed MR severity and other echocardiographic parameters at baseline and follow-up. The last patient has completed 5-year follow-up and the study is now closed.

A total of 55 patients were enrolled in the trial. The **MitraClip** device was implanted in 89% of patients and the trial met its pre-specified safety acceptance criterion, demonstrating mechanistic feasibility of implant and safety of the **MitraClip** System and procedure. There were no intra-procedural deaths. The procedure time averaged approximately 4 hours, patients were hemodynamically stable during the procedure, and the average length of hospital stay was approximately 3 days. A majority of patients (70.9%) experienced reduction in MR severity to 2+ or less at discharge. No **MitraClip** device embolizations occurred in this cohort. The rate of single leaflet device attachment (SLDA) in this initial cohort of patients treated was 10.2%. A majority of SLDAs were detected early (within 30 days post- **MitraClip** procedure). Patients demonstrated

Abbott

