improvement in NYHA Functional Class and left ventricular measurements that were sustained through 5 years. At 5 years, freedom from death was 86.4% and freedom from mitral valve surgery was 55.1%. The results of the EVEREST I trial at 5 years provide evidence of the safety and long-term durability of the **MitraClip** device in the early cohort of patients treated in the United States.

EVEREST II Randomized Controlled Trial (RCT) Design and Results

The EVEREST II RCT is a prospective, multi-center, randomized controlled trial in which patients with moderate-to-severe (3+) or severe (4+) MR were randomized in a 2:1 ratio between the Device group (**MitraClip** device) and the Control group (mitral valve surgery). Patient follow-up occurred at discharge, 30 days, 6, 12, 18 and 24 months and yearly thereafter through 5 years. An independent Echocardiography Core Laboratory (ECL) assessed MR severity and other echocardiographic parameters at baseline and follow-up. The trial was intended to demonstrate superiority of safety balanced against reduced effectiveness of the **MitraClip** device when compared to mitral valve surgery. All patients have completed 5 years of follow-up and the study is now closed.

The trial enrolled 279 patients: 184 in the Device group and 95 in the Control group. Of these, 178 patients in the Device group underwent the **MitraClip** procedure and 80 patients in the Control group underwent mitral valve surgery. The trial met both primary safety and effectiveness endpoints. There were no intra-procedural deaths. Among patients who underwent the **MitraClip** procedure in the Device group (**MitraClip** patients), a device was implanted in 89% of patients. The procedure time averaged approximately 3 hours, patients were hemodynamically stable during the procedure, and the average length of hospital stay was less than 3 days. In comparison, the average length of hospital stay for patients undergoing surgery in the Control group (surgery patients) was days. A large majority (94.9%) of **MitraClip** patients were discharged home without home healthcare. In comparison, 71.3% of surgery patients were discharged home without home healthcare. A majority of **MitraClip** device patients (77%) experienced reduction in MR severity to 2+ or less at discharge, while 100% of patients undergoing mitral valve surgery in the Control group experienced reduction in MR severity to 2+ or less.

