4.0 ENDPOINTS

4.1 Primary Endpoint

Successful implantation of the MitraClip NT device resulting in a decrease in the MR severity grade as assessed from the discharge echocardiogram (10-day echocardiogram will be used if discharge is unavailable or uninterpretable). Subjects who die or undergo mitral valve surgery before discharge will be considered a failure for the procedure.

Abbott

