5.2 Subject Screening

5.2.1 Subject Screening

The Principal Investigator at the site is responsible for screening subjects for the **MitraClip NT System** Russian Trial. All subjects must have a documented in-person consultation with the Cardiothoracic (CT) Surgeon investigator to assess surgical risk. The **MitraClip NT** implanter (who may also be the Principal Investigator) and a physician trained in echocardiography will also assess suitability of the subject for eligibility in the trial. These assessments combined are referred to as Site Heart Team. Refer below to the Table 1 for responsibilities.

Table 1. Responsibilities

| Role / Specialty | Responsibility |
|-----------------------------|--|
| Interventional Cardiologist | 
• Local Site Heart Team Member |

Abbott

CT Surgeon

- Screens potential subjects
- Performs **MitraClip NT** procedure*
- Local Site Heart Team Member
- Provides in-person assessment of surgical difficulty
- Local Site Heart Team Member
- Evaluates potential subjects for echocardiographic eligibility criteria
- Participates in the **MitraClip NT** procedure
- Perform required analysis of the TEE & TTE to complete the Case Report Form (CRF)

Potential patients will be fully informed about the clinical investigation, following the established Informed Consent process (described in [Section 5.2.2]). Once a duly dated and signed Informed Consent form is obtained, the clinical investigation-specific screening procedures may begin.

Subjects must be screened for clinical investigation eligibility by a member of the site's clinical investigation team previously trained to the CIP, and if applicable will be entered into a site-specific screening log.

In case the subject does not meet all inclusion criteria or meets any of the exclusion criteria, the subject is considered a screening failure. The Principal Investigator or the delegated clinical investigation personnel will record the screening failure in the hospital records and on a screening log as required.

Subject data will be collected following enrollment into the clinical investigation.

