5.3.2 Inclusion Criteria

5.3.2.1 General Inclusion Criteria

- Age 18 years or older.
- Symptomatic moderate-to-severe (3+) or severe MR (4+) chronic DMR or FMR determined by assessment of a qualifying transthoracic echocardiogram (TTE) obtained within 90 days or transesophageal echocardiogram (TEE) obtained within 180 days prior to subject registration.
 - LVEF \geq 30%
 - NYHA classification is class II, class III, or ambulatory class IV.
 - Subject is deemed difficult for mitral valve surgery due to either STS surgical mortality risk for mitral valve replacement of \geq 8% OR due to the presence of one of the following risk factors:
 - Porcelain aorta or mobile ascending aortic atheroma
 - Post-radiation mediastinum
 - Previous mediastinitis
 - Functional MR with LVEF $<$ 40%
 - Over 75 years old with LVEF $<$ 40%
 - Re-operation with patent grafts
 - Two or more prior cardiothoracic surgeries
 - Hepatic cirrhosis
 - Other surgical risk factor(s)
 - Mitral valve area \geq 4.0 cm².
 - The primary regurgitant jet is non-commisural, and in the opinion of the implanting investigator can successfully be treated by the MitraClip NT System. If a secondary jet exists, it must be considered clinically insignificant.

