- Withdrawal or Discontinuation

All subjects should continue to be monitored and treated per applicable standards of care consistent with the subject's condition. Subjects implanted with the **MitraClip NT** device must also be evaluated for device integrity.

The follow up visits (discharge, 10 day, and 30 day) will include following assessments. Additionally, these assessments will also be collected before any withdrawal or discontinuation of a subject.

Abbott

- Medical history
- Physical examination of the patient
- Weight, temperature, blood pressure and heart rate
- Concomitant cardiac medications including dose and reason(s) for any changes from Baseline
- CBC with differentials and platelet count
- Serum Creatinine
- Blood Urea Nitrogen (BUN)
- CK and CK-MB
- STS Mortality Risk Score for mitral valve replacement
- EuroScore II
- 12-lead ECG
- Transesophageal Echocardiography (TEE) – Screening, Discharge, 10 Days
- Transthoracic Echocardiography (TTE) – Screening, 10 Days, 30 Days
- NYHA Classification
- Six Minute Walk Test (6MWT) distance
- Modified Rankin Scalea
- Estimation NT Pro-BNP

Additional Follow-up Visits for All Subjects

Additional subject visits may occur as clinically warranted. The following information must be collected as applicable:

- Adverse events
- Concomitant Cardiovascular Medications including dosage, including clinical reasons for any changes
- Hospitalizations
- Mitral valve surgery
- Additional **MitraClip NT** procedure(s)

Additional Interventions for MR Reduction

It may be necessary for a subject to undergo additional interventions for MR reduction such as an additional **MitraClip NT** procedure or mitral valve surgery.

Requirements for this visit are as follows:

- Medical history
- Physical examination of the patient
- Weight, temperature, blood pressure and heart rate
- Concomitant cardiac medications including dose and reason(s) for any changes from Baseline
- CBC with differentials and platelet count
- Serum Creatinine
- Blood Urea Nitrogen (BUN)
- CK and CK-MB
- STS Mortality Risk Score for mitral valve replacement
- EuroScore II

MitraClip NT System
Clinical Investigation Plan Version: 1.0

Abbott

- 12-lead ECG
- Transesophageal Echocardiography (TEE)
- Transthoracic Echocardiography (TTE)
- NYHA Classification
- Six Minute Walk Test (6MWT) distance
- Modified Rankin Scalea
- Estimation NT Pro-BNP

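### The primary decrease in MR grade has no stated modality for the baseline or day-10 echo, a subject without an evaluable grade leaves the denominator, and follow-up measures are summarised only visit by visit

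*SAP*

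**What the plan says.** Protocol 4.1 defines success as implantation with a "decrease in the MR severity grade as assessed from the discharge echocardiogram", and lets the day-10 echo stand in when the discharge one is missing or cannot be read. SAP 1.4.1 and 2.3.1 repeat this; in SAP 2.3.1 the endpoint is a "decrease in the MR severity grade as assessed from the discharge echocardiogram (10-day echocardiogram will be used if discharge is unavailable or uninterpretable". Death or mitral valve surgery before discharge is a failure.

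The visits and modalities come from other sections:

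- Protocol 6.1, follow-up assessments: "Transesophageal Echocardiography (TEE) – Screening, Discharge, 10 Days" and "Transthoracic Echocardiography (TTE) – Screening, 10 Days, 30 Days". Table 4 in Protocol 6.2 agrees.
- Protocol 5.3.2.1: the qualifying grade is "determined by assessment of a qualifying transthoracic echocardiogram (TTE) obtained within 90 days or transesophageal echocardiogram (TEE) obtained within 180 days" before registration, so either modality can qualify a subject.
- Protocol 6.1 also requires a further TEE within 3 days before the procedure, to rule out mass, thrombus or vegetation.
- Protocol 5.2.1 gives a member of the site team the task to "Perform required analysis of the TEE & TTE to complete the Case Report Form (CRF". Both modalities are therefore read.

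On analysis, SAP 2.3.1 makes all registered subjects (the ATP) the primary population, while SAP 2.7 bases every analysis on available data. SAP 2.2 and 2.3.2 summarise continuous measures by number, mean and SD, and categorical ones by counts and percentages, with some items left to table mockups. Protocol 8.3 adds 95% confidence intervals for means and binary variables and plans no hypothesis test. SAP 1.4.2 lists the echo endpoints at baseline, discharge, day 10 and day 30 without modality.

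**The concern.** A decrease needs a before and an after. The text fixes the visit of the after grade but leaves open which modality supplies the before grade, and which supplies the after grade when day 10 is used. Two analysts could follow the SAP exactly and classify the same subject differently. Any drop in grade counts as success in a single arm of 16, so a single disagreement is visible in the result. If the choice is made after the grades are known, it can be made with the result in view.

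Two related gaps lie beside it. The explicit failure rule covers only death or mitral valve surgery before discharge, so an implanted subject with no evaluable post-procedure grade falls to SAP 2.7 and leaves the rate. And for measures collected repeatedly on the same subjects, the visible text reports each visit separately, which does not show how much subjects changed.

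**Working it through.** **1. Which modality is available when (Protocol 6.1 and 6.2)**

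| Visit | TEE | TTE |
|---|---|---|
| Screening/baseline | yes | yes |
| Discharge | yes | no |
| Day 10 | yes | yes |
| Day 30 | no | yes |

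The schedule implies TEE at discharge. The open items are the baseline grade and the day-10 grade. The TEE within 3 days of the procedure is a further possible baseline, though its stated purpose is not MR grading. A by-visit echo table under SAP 1.4.2 must set TEE at discharge beside TTE at day 30.

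**2. When the baseline modality changes a subject's result**

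Let L and H be the lower and higher of the two baseline grades (integer scale assumed). Success against H needs post < H; success against L needs post < L. The two differ only when L ≤ post < H:

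- 3+ and 4+: only at post = 3+.
- 2+ and 3+: only at post = 2+.
- 2+ and 4+: at post = 2+ or 3+.
- L = H: never.

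One reclassified subject moves the rate by 1/16 = 6.25 points. Exact 95% intervals: 16/16 = 100% (79.4 to 100); 15/16 = 93.8% (69.8 to 99.8); 14/16 = 87.5% (61.7 to 98.4). The sign is unknown because the documents give no TTE-TEE agreement data.

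**3. Effect of SAP 2.7 on the primary rate**

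Take one implanted subject with no evaluable post-procedure grade and 15 successes.

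- Excluded: 15/15 = 100%; lower limit 0.025^(1/15) = 78.2%.
- Counted as not successful: 15/16 = 93.8%; Clopper-Pearson 69.8 to 99.8.

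The rate differs by 6.25 points and the lower limit by 78.2 − 69.8 = 8.4 points.

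**4. What visit summaries leave out**

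Suppose 16 subjects have a baseline value and m of them a follow-up value. Then

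mean follow-up (m) − mean baseline (16) = [mean follow-up (m) − mean baseline (m)] + [mean baseline (m) − mean baseline (16)].

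The first bracket is change; the second is who was measured. With complete data the second is zero, but the SD of change, sqrt(s_b² + s_f² − 2·r·s_b·s_f), still needs the within-subject correlation r, which visit summaries do not give.

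For scale, with equal SDs and 16 pairs, the 95% half-width for mean change is t(15) × sqrt(2(1 − r)/16) SD, with t(15) = 2.131. An assumed r of 0.5 gives 0.53 SD; an assumed r of 0.8 gives 0.34 SD. These correlations are not in the documents.

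**The case against.** The strongest reply is that the schedule already supplies a matched pair. Every subject is due a baseline TEE and a discharge TEE, and a sensible analyst would use them. The CRF, which is not supplied, may identify the grade to use. No test and no visible threshold depends on one subject. This stands as a limit on size: naming the modality is close to a clarification. It does not answer the day-10 case or the missing-grade rule.

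A second reply is that the documents define the walk test, NYHA class and echo measures as values at visits, so visit summaries match the definitions, and the table mockups may contain more. That also stands. The lack of change summaries is a weakness of a descriptive plan, not an error in it. The visible SAP text invokes the mockups only for quartiles, extremes and exact intervals.

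Three stronger readings are tempting, and the documents do not support them.

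- *The success rate is inflated.* A modality difference could create a success or hide one; no figure shows which.
- *The earlier studies show how many subjects are exposed.* One might subtract the discharge results in Protocol 2.2.4 ("A majority of patients (70.9%) experienced reduction in MR severity to 2+ or less at discharge" in EVEREST I, "77%) experienced reduction in MR severity to 2+ or less at discharge" in the EVEREST II randomised trial) from the implant rates. For the latter, 89 − 77 = 12%, or 1.9 of 16, if both share a denominator; if the 77% refers to implanted patients, 0.89 × 0.23 = 20.5%, or 3.3 of 16. The subtraction also covers only baselines of 3+ and 4+, so it bounds nothing.
- *The plan wastes precision by treating visits as independent.* No between-visit comparison is planned at all.

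**Conclusion.** The point holds in limited form. The modality of the baseline grade and of the day-10 grade is unstated in both documents. The consequence is 6.25 points per reclassified subject, only where TTE and TEE disagree and the post-procedure grade falls between the two baseline readings; frequency and direction are unknown.

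The missing-data rule has a more definite effect. One subject without an evaluable grade turns 93.8% (69.8 to 99.8) into 100% (78.2 to 100), given that the other 15 succeed and that SAP 2.7 applies to the primary endpoint as written.

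The echo series mixes modalities between discharge and day 30 by schedule. Visit-only summaries on available data mix change with who was measured, subject to what the unseen mockups contain. These points should be settled before the grades are reviewed; they do not undermine the design.

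**What to change.** 1. **Protocol 4.1, SAP 1.4.1 and 2.3.1.** Compare the baseline TEE grade with the discharge TEE, or with the day-10 TEE when the discharge echo is missing or unreadable. State whether the TEE within 3 days of the procedure serves as baseline when the screening TEE cannot be graded. Do not replace a readable discharge TEE with a day-10 TTE; that would contradict the endpoint's own order of use. Flag any cross-modality comparison in the listing.
2. **SAP 2.3.1 and 2.7.** For the primary endpoint, keep all registered subjects in the denominator and count a subject with no evaluable post-procedure grade as not successful. Show the available-data rate as a sensitivity analysis.
3. **SAP 1.4.2 and 2.3.2, echo tables.** Tabulate by modality, with 30-day TTE against baseline TTE.
4. **SAP 2.2 and 2.3.2.** Beside the visit summaries, give within-subject change with the number of pairs and a 95% confidence interval for the walk test and continuous echo measures, and baseline-to-visit shift tables for MR grade and NYHA class.

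The cost is protocol and SAP wording and table shells; every echo and test named is already scheduled. Item 2 is a change of rule, not just a clarification, and may lower the reported rate slightly. Subjects without a pair drop out of the change summaries. Pairing does not remove informative dropout, reader variation, or regression to the mean where the qualifying echo is also the baseline.

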#### 2.3.2 Descriptive Endpoints

The analyses for the descriptive endpoints will be performed using the methods described in Section 2.2 for ATP populations.

### 2.4 Sample Size Calculations

Sixteen (16) DMR or FMR patients will be registered in the study. This sample size is determined based on the primary endpoint of successful implantation of the MitraClip NT device resulting in a decrease in the MR severity grade as assessed from the discharge echocardiogram.

[REDACTED]

[REDACTED]

[REDACTED]

[REDACTED]

Therefore, a sample size of 16 subjects ensure an observed rate that is readily interpretable.

### 2.5 Timing of Analysis

The primary endpoint analyses will be performed when all subjects complete their 30-day follow-up.

### 2.6 Subgroups for Analysis

No subgroup analyses are planned for this clinical investigation.

## Statistical Analysis Plan

### 2.7 Handling of Missing Data

All analyses will be based on available data with missing data excluded. Any unused or spurious data will be noted as appropriate in the final report.

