5.4.1 Subject Registration

A subject is considered registered when after enrolment and screening procedures it has been confirmed that the subject meets all inclusion criteria and none of the exclusion criteria and upon femoral vein puncture for transseptal access in preparation for the **MitraClip NT System** insertion.

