Administer additional intravenous doses of antibiotics at approximately 6 and 12 hours (or per institutional guidelines) after the completion of the procedure.

Subjects will receive standard post-cardiac catheterization procedure care as judged appropriate by the Investigator.

Subject weight, blood pressure, heart rate and temperature must be obtained prior to subject discharge from the hospital.

At discharge, each subject implanted with a **MitraClip NT** device(s) must be provided an Implant Identification Card. An Implant Identification Card is included in the package with each **MitraClip NT** System. The subject must be instructed to keep this Implant Identification Card on their person at all times. The serial number of all implanted **MitraClip NT** device(s) must be recorded on the Implant Identification Card.

The Investigator must instruct all subjects who receive the **MitraClip NT** device of the need for prophylaxis for endocarditis, as recommended in the guidelines for the prevention and treatment of infective endocarditis. Subjects must be instructed to notify the Investigator or the subject's primary care physician in the event that a procedure recommended by this Guideline is planned, so that prophylactic antibiotics can be prescribed. Post- **MitraClip NT** procedure anticoagulation is recommended per the Investigator's discretion as follows:

1. Reinitiate warfarin, dabigatran or factor Xa inhibitor (if discontinued for the **MitraClip NT** procedure) at pre-procedure levels or as appropriate. If chronic oral anticoagulation is used, then aspirin and ticlopidene use are not recommended, but are allowed if otherwise indicated for other conditions.
2. If chronic oral anticoagulation is not used, it is strongly recommended that either daily ticlopidene and/or aspirin (81 mg) is administered for 6 months or longer. If aspirin is to be used, a dose of 325 mg acetylsalicylic acid (ASA) may be administered either pre- or immediately post- **MitraClip NT** procedure followed by 81 mg per day for 6 months or longer per Institutional standards and at the discretion of the Investigator.

Follow-up for All Subjects

Clinical follow-up will be performed at the following intervals for all enrolled subjects, regardless of whether a **MitraClip NT** device was successfully implanted:

Discharge post- **MitraClip NT procedure**

- 10 days follow-up office visit (this visit must be conducted even if subject is in hospital);
- 30 days.

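### Excluding missing echocardiograms from the primary endpoint, and ending the failure window at discharge when the echo may be read at day 10, may overstate the success rate

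*SAP*

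**What the plan says.** - **Missing data.** SAP 2.7: "All analyses will be based on available data with missing data excluded". It adds only that unused or spurious data will be noted in the final report. No analysis is exempted and no sensitivity analysis is planned.
- **Echo used.** Protocol 4.1, repeated in SAP 1.4.1 and 2.3.1, defines success as implantation that lowers the MR grade on the discharge echo, with a fallback: "10-day echocardiogram will be used if discharge is unavailable or uninterpretable".
- **Failure rule.** "Subjects who die or undergo mitral valve surgery before discharge will be considered a failure for the procedure" (SAP 2.3.1; same rule in Protocol 4.1).
- **Population.** SAP 2.3.1 names the Attempted Procedure Population (ATP). SAP 2.1.1 defines it as eligible registered patients, and having an echo is not a condition. Protocol 5.4.1 places registration "upon femoral vein puncture for transseptal access in preparation for the" device insertion.
- **Echo schedule.** Protocol 6.1 lists "Transesophageal Echocardiography (TEE) – Screening, Discharge, 10 Days" and "Transthoracic Echocardiography (TTE) – Screening, 10 Days, 30 Days". Table 4 in Protocol 6.2 agrees: TEE is the only echo at discharge, and day 10 has both.
- **Reporting.** SAP 2.2.2: "For binary variables such as adverse events, results will be summarized with patient counts, and percentages". Exact Clopper-Pearson intervals are given where the table mock-ups call for them.

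**The concern.** The endpoint assessment can move to day 10, but the failure rule does not move with it, and SAP 2.7 removes whoever is left without an echo. Three kinds of subject are affected:

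1. Discharged without a usable discharge echo, then dies before the 10-day echo. No data exist, so the subject is excluded rather than failed.
2. Discharged without a usable discharge echo, then has mitral valve surgery before day 10. The 10-day echo then shows the surgical result and could be scored as a success.
3. Registered and implanted, but neither echo is usable. The subject leaves the denominator although still a member of the ATP.

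This rate is the primary result of a 16-subject, single-arm study without a hypothesis test, so the point estimate and its interval are the finding. SAP 2.4 defends the sample size on the ground that the observed rate will be easy to interpret. That is harder to sustain if the denominator can shrink in a way related to outcome.

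**Working it through.** **Inputs.** N = 16 registered (Protocol 5.7, SAP 2.4). The assumptions behind N are redacted and there is no test, so N cannot be reproduced; this is not a fault of the plan. The documents give no rate of missing echoes, so the number excluded, k, and the number of observed failures, f, are assumptions.

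**Who is affected.** With a usable discharge echo, the endpoint is fixed at discharge and later events do not alter it. Deaths and surgery before discharge are already failures. That includes a subject still in hospital at day 10, when "this visit must be conducted even if subject is in hospital". A subject with no clip cannot meet an endpoint that requires successful implantation. What remains is the three cases above.

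**Effect on the rate.** Let s = 16 − k − f.

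- Available data (SAP 2.7): s/(16 − k)
- Missing counted as failure: s/16
- Missing counted as success: (s + k)/16

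| f | k | Available data (exact 95% CI) | Missing = failure (exact 95% CI) | Missing = success |
|---|---|---|---|---|
| 0 | 1 | 15/15 = 100% (78.2–100) | 15/16 = 93.8% (69.8–99.8) | 100% |
| 0 | 2 | 14/14 = 100% (76.8–100) | 14/16 = 87.5% (61.7–98.4) | 100% |
| 1 | 1 | 14/15 = 93.3% (68.1–99.8) | 14/16 = 87.5% (61.7–98.4) | 93.8% |
| 1 | 2 | 13/14 = 92.9% (66.1–99.8) | 13/16 = 81.3% (54.4–96.0) | 93.8% |
| 2 | 2 | 12/14 = 85.7% (57.2–98.2) | 12/16 = 75.0% (47.6–92.7) | 87.5% |

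Each exclusion costs about 5 to 6 points if the subject was a true failure. With no observed failure, the available-data rate stays at 100% however many are missing. One post-surgical echo scored as a success adds 1/16 = 6.25 points.

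**Chance that anyone is dropped.** If q is the chance that a subject has neither echo, P(at least one of 16) = 1 − (1 − q)^16. Assumed q of 2%, 5% and 10% gives 28%, 56% and 81%. If instead each visit failed independently in 5% or 10% of subjects, q would be 0.05² = 0.25% or 0.10² = 1%, and the chance about 4% or 15%. Correlation between visits would raise these.

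**Direction.** Let p be the true success rate, and m_f and m_s the shares missing among failures and successes. The expected available-data rate is p(1 − m_s) / [p(1 − m_s) + (1 − p)(1 − m_f)]. For illustration p = 0.77, the EVEREST II discharge figure in Protocol 2.2.4 for MR of 2+ or less, which is a different endpoint:

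- m_f = 20%, m_s = 5%: 0.7315/(0.7315 + 0.1840) = 79.9%
- m_f = m_s = 10%: 77.0%
- m_f = 5%, m_s = 10%: 0.6930/(0.6930 + 0.2185) = 76.0%

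**Deaths in the gap.** Spread the 7.7% 30-day mortality of the High Risk Registry (Protocol 2.2.4) evenly over 30 days and assume discharge on day 4, so that six days remain to day 10: 0.077 × 6/30 × 16 = 0.25 expected deaths. Only those without a usable discharge echo are lost. If that is 5–20% of subjects, independently of death, the expected number lost is about 0.01 to 0.05.

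**The case against.** The strongest reply is that the gap will seldom matter and the text already half closes it.

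- **Post-surgical echo.** The endpoint requires that the lower MR grade result from implantation, so a decrease produced by surgery arguably does not qualify. Eligible subjects are also judged difficult for surgery. This weakens the case, but no rule says how to score such an echo.
- **Count, not percentage.** SAP 2.3.1 speaks of the number of successes in the ATP, which can be read as x of 16. The count is indeed not inflated by an exclusion. But SAP 2.2.2 also reports percentages, and SAP 2.7 governs their denominator.
- **Few missing echoes.** Day 10 offers both TEE and TTE, and Protocol 6.1 asks for the follow-up assessments before any withdrawal. Both reduce missingness. Still, a subject without a usable discharge TEE depends wholly on day 10, and Protocol 5.6 limits data after withdrawal to vital status.
- **Deaths in the gap are rare.** This stands, on the figures above.
- **Other reporting.** Mortality, implant rate, mitral valve surgery and MR grade by visit are reported separately, counts accompany percentages, and no stated decision threshold depends on the rate. A reader could notice a smaller denominator, but the primary rate would not be corrected.
- **Choice of remedy.** Counting missing as failure biases the rate downward if missingness is unrelated to outcome. This is fair, and it is why the available-data rate should be kept alongside.

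These points limit how often the problem arises. None of them says how the affected subjects are to be counted.

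**Conclusion.** The concern holds and should be fixed. Followed as written, SAP 2.7 removes an implanted subject with neither echo from the primary denominator, and the failure window closes before the fallback echo is taken. The larger exposure is the subject with neither echo; the interval between discharge and day 10 is a real mismatch but will rarely be populated.

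The 5-to-6-point effect per exclusion is a worst case that takes every excluded subject to be a true failure. If they were successes, the available-data rate would be equal or slightly low (14/15 = 93.3% against 15/16 = 93.8%). The numbers of missing echoes and failures are assumed throughout. Confidence is high about the rule and its consequence for a given excluded subject, not about the size or direction of bias in this study.

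**What to change.** 1. **Protocol 4.1, SAP 1.4.1 and 2.3.1.** State that a subject is a failure if no clip is implanted, or if death or mitral valve surgery occurs before the echocardiogram actually used for the endpoint.
2. **SAP 2.7.** State that the available-data rule does not apply to the primary endpoint, that the denominator is all registered subjects, and that a subject with no evaluable discharge or 10-day echo counts as a failure. Report the available-data rate as a sensitivity analysis, with the number excluded and the reasons; the missing-as-success bound can be added at no cost.
3. **Alongside the primary result.** Report any repeat MitraClip procedure before the echo used, without redefining the endpoint.
4. **SAP 2.1.1, clarification only.** Say that the ATP is all registered subjects, and list any eligibility deviations found later.

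The cost is SAP text plus a protocol wording change that needs ethics committee handling under Protocol 10.3 and 12.0. No new data are collected. The reported rate may be slightly less favourable. The rule should be settled before outcomes are seen, so that the handling of one or two subjects is not decided afterwards.
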